6.2.16. Pharmacokinetics

Per the SOE, sparse PK sampling will be collected at sites that are able to obtain and process PK samples. Day 5 blood collection may be used to measure drug levels to assess the relationship between drug exposure and viral elimination dynamics including time to clearance.

When possible, participants should fast overnight before their Day 5 visit (i.e., participants should arrive at the Day 5 visit having had no food or drink intake except for water in the previous 8 hours).

Specifically, blood will be collected for sparse PK measurements at the following timepoints, where possible:

- Just prior to the morning dose on Day 5 (trough)
- Approximately 1-hour post morning dose on Day 5
- Approximately 2-hours post morning dose on Day 5 (if possible)

The timing of the post-dose samples may be adjusted for individual participants to increase the range of timepoints for PK evaluation. No participant will have more than 3 PK samples taken. The approximate time of the 3 doses preceding the PK sampling, the exact time of the dose

immediately preceding the PK sample, the time of the most recent meal, and the exact time of each PK sample collection should be recorded.

If it is determined that sufficient PK samples have been collected to characterize the PK profile in this patient population, PK sample collection may be discontinued by the Sponsor at any time.

7. ADVERSE EVENTS AND STUDY MONITORING

7.1. **Definition of Adverse Events**

An AE is any unfavorable and unintended sign (including an abnormal laboratory finding), symptom, or diagnosis that occurs in a study participant during the conduct of the study REGARDLESS of the attribution (i.e., relationship of event to medical treatment/study product/device or procedure/intervention). This includes any occurrence that is new in onset or aggravated in severity or frequency from the baseline condition. The principal investigator (PI) and medical monitor will review all AEs on a weekly basis to determine which are treatment-related AEs.

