7.3.3. Relationship

The relationship of an AE to the administration of the study drug is to be assessed by the investigator according to the following definitions:

- No (unrelated, not related, no relation): The time course between the administration of study drug and the occurrence or worsening of the AE rules out a causal relationship and another cause (concomitant drugs, therapies, complications, etc.) is suspected.
- Yes (related): The time course between the administration of study drug and the occurrence or worsening of the AE is consistent with a causal relationship and no other cause (concomitant drugs, therapies, complications, etc.) can be identified.

The following factors should also be considered:

- The temporal sequence from study drug administration The event should occur after the study drug is given. The length of time from study drug exposure to event should be evaluated in the clinical context of the event.
- Underlying, concomitant, intercurrent diseases Each report should be evaluated in the context of the natural history and course of the disease being treated and any other disease the participant may have.
- Concomitant medication The other medications the participant is taking or the treatment the participant receives should be examined to determine whether any of them might be recognized to cause the event in question.
- Known response pattern for this class of study drug Clinical and/or preclinical data may indicate whether a particular response is likely to be a class effect.
- Exposure to physical and/or mental stresses The exposure to stress might induce adverse changes in the recipient and provide a logical and better explanation for the event.
- The pharmacology and pharmacokinetics of the study drug The known pharmacologic properties (absorption, distribution, metabolism, and excretion) of the study drug should be considered.

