7.3.4. Expedited AE Reporting Period

- Any medical condition that is present at the time that the participant is screened will be considered as baseline and not reported as an AE. However, if any pre-existing medical condition increases in severity after starting study treatment, it should be recorded as an AE.
- Although disease progression including hospitalization for COVID-19 will be collected as AEs, SAEs of disease progression will be considered expected for EIDD-2801 in this protocol and will not be reported as SUSARs.

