- Participants with Grade 3 or 4 asymptomatic creatine kinase (CK) elevation may continue study medication if the investigator has evidence that the CK elevation is not suspected to be related to the study medications.
- Participants with new Grade 3 or 4 AEs that are considered to be COVID-19 related and not study product related may continue study product following discussion with one of the study team leads.

8.6. **Pregnancy**

The study products may not be given in pregnancy.

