10.7.3.1. Primary Outcome Measures

Virologic Efficacy: The distribution of days until first non-detectable SARS-CoV-2 viral RNA in NP swabs will be estimated for each randomized arm (drug versus placebo), using Kaplan-Meier methods with a corresponding exact stratified log-rank test (Part 1 only: to account for the "early" versus "late" time from symptom onset randomization strata). "Non detectable" will be defined as a viral load below the limit of quantification (BLOQ). Two consecutive non-detectable viral RNAs in NP swabs (or one negative with no further follow-up) will be required to achieve the event. The date of the first non-detectable will be the event date. Participants who prematurely discontinue the study before achieving non-detectable results will have follow-up for efficacy endpoints censored at the date of last measurement. Losses to follow-up will be assumed non-informative.

Safety and Tolerability: In order to measure the safety and tolerability of EIDD-2801, we will estimate by randomization arm the probability of 1) any AEs leading to early discontinuation of blinded treatment (active or placebo), 2) study drug-related discontinuation of treatment, 3) new grade 3 or higher AE (not already present at baseline), and 4) study drug-related new grade 3 or higher AE. The cumulative probability (i.e., risk) of each safety and each tolerability endpoint (4 endpoints) will be estimated using the Kaplan-Meier approach and stratified log-rank test will be employed for between trial arm comparisons (as outlined for the primary efficacy outcome). Follow-up will be right censored at the date of last known status and event times will be the date of first onset of the given endpoint (e.g., time to first AE leading to early discontinuation of blinded treatment).

The safety and tolerability profile of EIDD-2801 in humans is currently not fully characterized and descriptive participant-level listings of safety and tolerability events will be summarized. We will estimate 28-day risk function of each safety and tolerability endpoint with a corresponding 2-sided 90% confidence interval, with focus on the upper confidence limit for interpretation of results. To inform the design of future larger trials we will estimate the difference in probabilities

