8.2. Adverse Events

Adverse events will be coded using MedDRA[®] (Medical Dictionary for Regulatory Activities) Version 23. Any events reported after the initiation of study treatment and up to 14 days after the last dose of study treatment are defined as treatment-emergent AEs (TEAEs). AEs started more than 14 days after the last dose of study treatment will be considered post treatment and will be summarized separately

Adverse event summarizes will summarize only TEAEs. Adverse events will be categorized by TEAE, serious TEAE (SAE), death, and discontinuation. These categories will be further summarized by the causal relationship to study drug (Related and Possible related will be grouped together as Related; AEs Reported as Unlikely and Not Related will be grouped together as Not Related).

The Investigator will provide an assessment of the intensity of each AE. Intensity will be assessed in terms of severity (mild, moderate, severe, potentially life-threatening or death). Subjects will be counted once and summarized under their highest severity within a SOC and PT.

The following TEAE summary tables will be prepared:

• Overall Summary of TEAEs (Any TEAE, TEAE Related to study drug, Grade 2 or higher TEAE, Grade 3 or higher TEAE, Drug related TEAEs, Drug related Grade 3 or higher

TEAE, TEAEs leading to study drug discontinuation, Drug related TEAEs leading to study drug discontinuation, Serious TEAE, TEAE leading to death)

- Summary of TEAEs by SOC and PT
- Summary of TEAEs by maximum severity SOC, and PT
- Summary of Grade 2 or higher TEAEs by SOC and PT
- Summary of Grade 3 or higher TEAEs by SOC and PT
- Summary of Drug Related Grade 3 or higher TEAEs by SOC and PT
- Summary of Drug Related TEAEs by SOC, and PT
- Summary of TEAEs resulting in discontinuation from study drug by SOC and PT
- Summary of Drug Related TEAEs resulting in discontinuation from study drug by SOC and PT
- Summary of Serious TEAEs by SOC and PT
- Summary of Drug Related Serious TEAEs by SOC and PT
- Summary of Post Treatment AEs by SOC and PT

8.3. **Pregnancies (as applicable)**

If any female subjects become pregnant during the study, a listing will be provided.

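### COVID-19 progression counts as an adverse event, so antiviral benefit can partly offset drug toxicity in the all-cause Grade 3+ and Grade 2+ safety rates, and no planned table separates the two

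*Protocol*

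**What the plan says.** Protocol Section 7.1 counts any unfavourable event whatever its cause, and adds: "This includes any occurrence that is new in onset or aggravated in severity or frequency from the baseline condition". Section 7.3.4 applies this to conditions present at screening: "if any pre-existing medical condition increases in severity after starting study treatment, it should be recorded as an AE". It then names the disease under study: "Although disease progression including hospitalization for COVID-19 will be collected as AEs". Its only exemption is that serious events of disease progression are not reported as SUSARs. The list at the end of Section 8.5 shows that such events can reach the top grades, since it refers to "Participants with new Grade 3 or 4 AEs that are considered to be COVID-19 related and not study product related".

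The primary safety endpoints in Section 10.7.3.1 include "new grade 3 or higher AE (not already present at baseline), and 4) study drug-related new grade 3 or higher AE". Section 10.7.3.2 treats Grade 2 or higher AEs and drug-related AEs as secondary, by the same approach. None of these definitions excludes COVID-19 events.

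SAP 8.2 defines treatment-emergent AEs by time window alone and lists tables such as "Summary of Grade 3 or higher TEAEs by SOC and PT". No table sets COVID-19 progression apart from other AEs.

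On causality, Protocol 7.3.3 uses Yes/No. Yes requires a compatible time course and that "no other cause (concomitant drugs, therapies, complications, etc.) can be identified". SAP 8.2 uses four levels: Related and Possibly related are grouped as Related, and Unlikely and Not Related as Not Related.

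**The concern.** Hospitalization for COVID-19 and clinical progression are efficacy outcomes here: hospitalization by Day 28 is a secondary objective and the progression composite is exploratory. The same events also feed the all-cause Grade 3+ and Grade 2+ safety rates. If the drug works, the active arm loses some of these events, and its all-cause AE rate falls for a reason unrelated to tolerability. Toxicity of similar size could then leave the two arms looking alike. A reader of the primary safety table would see the net of benefit and harm and could not recover the harm from it.

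**Working it through.** **No figure to reproduce.** Neither document gives an event rate, precision target or power for any safety endpoint. The structure follows from the definitions above. The arithmetic below only shows how large the offset could be.

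**Inputs**
- *p*, placebo risk of a Grade 3+ COVID-19 AE: not given, so assumed at 2% to 19%. The top of the range is the 14% severe plus 5% critical in Protocol 2.1.1. Those figures describe symptomatic patients generally, whereas Section 4.2.1 excludes anyone needing hospitalization or immediate medical attention, so 19% is an upper anchor.
- *r*, relative reduction of that risk by the drug: assumed 30% or 50%.
- *t*, added Grade 3+ risk from toxicity, independent of COVID-19 events: assumed.
- Group sizes: 22 v 22 in Part 1; 118 v 54 pooled (Protocol Section 3 table).

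**Formulas.** With no other background events, the placebo risk is p and the active risk is 1 − (1 − p(1 − r))(1 − t). Setting the difference to zero gives the toxicity that is fully offset: t = pr / (1 − p(1 − r)).

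| Placebo COVID-19 Grade 3+ risk | Offset, r = 30% | Offset, r = 50% |
|---|---|---|
| 2% | 0.006/0.986 = 0.6% | 0.010/0.990 = 1.0% |
| 5% | 0.015/0.965 = 1.6% | 0.025/0.975 = 2.6% |
| 10% | 0.030/0.930 = 3.2% | 0.050/0.950 = 5.3% |
| 19% | 0.057/0.867 = 6.6% | 0.095/0.905 = 10.5% |

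With r = 0 nothing is offset.

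**Examples with t = 5%**
- p = 5%, r = 30%: active 1 − 0.965 × 0.95 = 8.3%, difference +3.3 points.
- p = 10%, r = 50%: active 1 − 0.95 × 0.95 = 9.75%, difference −0.25 points.
- p = 15%, r = 50%: active 1 − 0.925 × 0.95 = 12.1%, difference −2.9 points.

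**Effect on an interval.** For Part 1, Protocol 10.7.3.1 plans a 90% interval for the risk difference. Take p = 10%, t = 5% and a Wald interval, difference + 1.645 × √[p₁(1 − p₁)/n₁ + p₀(1 − p₀)/n₀]. At 22 v 22 the upper limit is 20.7 points with no antiviral effect (14.5% v 10%) and 14.5 points with r = 50% (9.75% v 10%). At 118 v 54 it falls from 13.1 to 7.8 points. The pooled analyses plan 95% intervals (Section 10.8), so the second pair is illustrative. The SAP specifies no interval for safety, so this matters only if the protocol's interval is still reported.

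**The case against.** All-cause counting is internally consistent, and the plan contains real safeguards.

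- **No test is affected.** SAP 2.3 and 11 make safety descriptive. This stands: the effect is on side-by-side rates only.
- **Drug-related endpoints.** A reader might infer from the Yes definition in Protocol 7.3.3 that these endpoints are useless in people with active COVID-19. The documents do not support that. The No definition requires the time course to rule out causality, so an event with compatible timing and COVID-19 as another possible cause meets neither definition. SAP 8.2 puts possibly related events with related ones, and SAP 5.6 counts missing relationship as probably related. What remains is that the two scales differ, so the sensitivity of these endpoints is unsettled.
- **Preferred-term rows.** Protocol 7.3 asks for diagnoses rather than symptoms where possible, so progression would often have its own row. This helps. But one participant can appear in several rows, so they cannot be added up to the proportion with any Grade 3+ event other than progression. Single symptoms also overlap: headache and diarrhea were the most frequent phase 1 AEs (Protocol 2.6), and both are on the symptom list in SAP 5.5.3.
- **Other displays.** Listings, graded laboratory tables (SAP 8.4), the hospitalization summary (SAP 9.5) and the composite (SAP 9.6) each show part of the picture.
- **Precision.** In Part 1, 5% toxicity is about one event (22 × 0.05 = 1.1), which would be judged from listings. This stands.
- **Dose choice.** A reader might infer that netted rates will drive dose selection. Protocol 10.9 says only that unblinded virology and safety data may be reviewed. It does not say that these rates decide.

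**Conclusion.** The all-cause Grade 3+ and Grade 2+ rates mix drug toxicity with events the drug should reduce, and no planned table gives the subject-level rate without COVID-19 progression. Existing displays mitigate this only in part.

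The size cannot be fixed from the documents. Under the assumptions above, the fully offset Grade 3+ toxicity is 1 point or less at a 2% COVID-19 event rate and up to about 10.5 points at 19%. It depends on independent risks and no other background events. No comparable range is offered for Grade 2+.

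A reader might conclude that toxicity will be fully hidden. That goes too far: the −0.25 point example places 5% toxicity almost at its break-even of 5.3%, and the low example still shows +3.3 of the 5 points. What is supported is a possible partial offset of unknown size, worth a low-cost change to the tables.

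**What to change.** In SAP 8.2, keep the all-cause Grade 2+ and Grade 3+ tables. Beside each, add a supplementary table with the same layout, including the any-event row, that excludes COVID-19 progression events.

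Define the exclusion by a list of MedDRA terms fixed in a blinded review before any unblinded analysis, including the planned one after Parts 1-6 (SAP 4.1). A term list is preferable to investigator attribution, which could remove ambiguous symptoms that are in fact toxicity. For the same reason, keep non-specific symptoms that overlap with possible drug effects, such as headache, nausea and diarrhea, in the supplementary table. State that the two tables are interpreted together.

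Reconcile the causality scale between Protocol 7.3.3 and SAP 8.2, and say which one the case report form collects.

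The cost is two more tables, one blinded review of terms, and a judgement on what counts as progression. That judgement is the reason for keeping the all-cause tables.

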7.2. Adverse Event Collection Requirements for This Protocol

Post-entry, all AEs must be recorded on the eCRFs within 72 hours if any of the following criteria have been met:

- All Grade ≥ 2 AEs
- All AEs that led to a change in study treatment/intervention regardless of grade

The PI or clinical site personnel should notify Covance Patient Safety Solutions (PSS) of all SAEs, regardless of relationship to the investigational drug, within 24 hours of clinical site personnel becoming aware of the event. The PI (or designee) will provide the initial notification by sending a completed SAE form which must include the PI's (or designee's) assessment of the relationship of the event to investigational drug and must be signed by the PI. Follow-up information, or new information regarding an ongoing SAE, must be provided promptly to Covance Drug Safety Services (DSS) at [contact] or via fax.

The SAE Form will collect data surrounding the event (e.g., the nature of the symptom[s], time of onset in relation to initiation of therapy, duration, intensity, and whether or not therapy was interrupted or discontinued). The Investigator's assessment of the probable cause of the event will also be included. In addition, relevant medical history, concomitant medications, laboratory and diagnostic tests reports, and procedures as well as all pertinent medical information related to the event will also be collected.

All AEs that are reported must have their severity graded. To grade AEs, sites must refer to the DAIDS AE Grading Table, corrected Version 2.1, July 2017, which can be found on the DAIDS RSC website at https://rsc.niaid.nih.gov/clinical-research-sites/daids-adverse-event-grading-tables.

Serious Adverse Events (SAEs)

An SAE is defined as any untoward medical occurrence that:

- Results in death
- Is life-threatening illness
- Requires inpatient hospitalization or prolongation of existing hospitalization.
- Results in persistent or significant disability/incapacity.

- Is a congenital anomaly/birth defect, or
- Is an important medical event that may not be immediately life-threatening or result in death or hospitalization but may jeopardize the patient or may require intervention to prevent one of the other outcomes listed in the definition above).

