2.4. Evidence in Humans

EIDD-2801 has not been used prophylactically or therapeutically in patients with COVID-19; however, EIDD-2801 has been studied in a single and multiple ascending dose study in healthy volunteers (Study EIDD-2801-1001). Preliminary data from this study showed that doses of 200 mg produce plasma levels of EIDD-1931 that are predicted to show antiviral activity in humans. A brief summary of safety information from Study EIDD-2801-1001 is provided in Section 2.6.

2.5. **Potential Risks and Benefits**

There remains unmet medical need for the treatment of COVID-19, particularly in outpatients where intravenous administration of antiviral therapy is difficult. Participants in this study will be monitored throughout the 5-day treatment course and follow-up period with surveillance for and reporting of all AEs.

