10.3. Objectives and Endpoints

Objectives	Endpoints
Prir	nary
To determine if EIDD-2801 reduces the time to viral RNA negativity. Viral RNA negativity will be determined by RT-PCR of NP swabs.	• Qualitative RT-PCR
To determine the safety and tolerability of EIDD-2801 including 1) any adverse events (AEs) leading to early discontinuation of treatment, 2) study drug-related discontinuation of treatment, 3) new grade 3 or higher AE (not already present at baseline), and 4) study drug-related new grade 3 or higher AE.	 All AEs leading to early discontinuation of treatment Study drug-related discontinuation of treatment New grade 3 or higher AE Study drug-related new grade 3 or higher AE

Secon	ndary
Safety Objective: To compare the incidence of grade 2 or higher AEs and drug-related AEs between treatment arms.	Grade 2 or higher AEsDrug-related AEs
Virologic Objectives:	
• To determine if EIDD-2801 reduces the time (days) to negativity of infectious virus isolation in NP swabs from SARS-CoV-2-infected adults. Infectious virus isolation is determined by isolation in Vero cell line cultures.	 Infectious virus detection in NP swab samples cultured on Vero-cell cultures Infectious virus detection by microfoci assay of NP swab samples cultured on Vero-cell cultures
• To determine if EIDD-2801 reduces the shedding of SARS-CoV-2 RNA in NP swabs compared to placebo as measured by median change in RNA at Treatment Days 3, 5, 7, 14, and 28 as determined by quantitative RT-PCR.	• Quantitative RT-PCR
• To determine if EIDD-2801 increases viral RNA mutation rate. RNA mutation rate is measured by Next Generation sequencing.	• Comparison of spike and RNA dependent RNA polymerase gene sequences using Next Generation sequencing
Clinical Objectives:	Patient reported symptoms
• To determine if EIDD-2801 changes the severity and duration of self-reported symptoms of COVID-19	• Time to improvement of new or worsened symptoms (including feverishness, chills, myalgias, headache, sore throat, loss of sense of smell, loss of sense of taste, cough, and difficulty breathing) as measured by a decrease in all of these symptoms from severe/moderate severity to mild/absent or a decrease in mild severity to absent in symptom diary (Absent or returned to pre- COVID-19 level = 0, Mild =1, Moderate =2, Severe =3).

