10.7.3.2. Secondary Outcomes

Safety: Occurrence of Grade 2 or higher AEs and drug related AEs will be evaluated using the same approach as outlined for the primary safety analysis in Section 10.7.3.1. We will describe and estimate all-cause mortality and hospitalization during the 28-day period from and including the day of the first (confirmed) dose of study treatment. The Kaplan-Meier approach described above will be applied to the endpoint of days until first hospitalization or death, and the 28-day risk function will be estimated as described for the primary safety endpoints.

Duration of fever, duration of symptoms, and duration of time to self-reported return to usual health will be summarized with descriptive statistics. Participant-specific durations of fever and symptoms will be compared between study arms using a stratified Wilcoxon rank-sum test. The distribution of days until improvement of all new or worsened COVID-19 symptoms will be compared between study arms using Kaplan-Meier methods with a corresponding exact stratified log-rank test (to account for the "early" versus "late" time from symptom onset randomization strata). New or worsened symptoms of COVID-19 may include feverishness, chills, myalgias, headache, sore throat, loss of sense of smell, loss of sense of taste, cough, and difficulty breathing. Improvement in these symptoms is defined as a decrease in all new or worsened symptoms (i.e., from severe/moderate severity to mild/absent/pre-COVID-19 severity, or a decrease in mild severity to absent). Participants who do not have complete symptom diaries due to hospitalization or death will be ranked in these analyses as having poorer outcomes than participants who survived without hospitalization.

Analyses for the additional objectives will be described in the SAP.

Virologic: The distribution of days until first non-detectable SARS-CoV-2 in NP swabs (i.e., infectious virus measurement) will also be estimated for each randomized arm (drug versus placebo), using Kaplan-Meier methods with a corresponding exact stratified log-rank test (to account for the "early" versus "late" time from symptom onset randomization strata). Participants who prematurely discontinue the study before achieving nondetectable results will have follow-up for efficacy endpoints censored at the date of last measurement. Losses to follow-up will be assumed non-informative.

Protocol EIDD-2801-2003 Ridgeback Biotherapeutics LP

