2.2.2. Secondary Endpoint

- Incidence of Grade 2 or higher AEs and drug-related AEs
- Infectious virus detection in NP swab samples cultured on Vero-cell cultures
- Comparison of spike and RNA dependent RNA polymerase gene sequences using Next Generation sequencing
- Patient reported symptoms of COVID-19
- WHO 9-point ordinal scale
- Concentrations of EIDD-2801 and EIDD-1931

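### Protocol 7.2 does not oblige sites to record Grade 1 AEs that leave treatment unchanged, yet the drug-related AE endpoint and several SAP tables have no grade floor

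*Protocol*

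**What the plan says.** Protocol 7.2, the section on AE collection requirements, states: "Post-entry, all AEs must be recorded on the eCRFs within 72 hours if any of the following criteria have been met". Two criteria follow: "All Grade ≥ 2 AEs" and "All AEs that led to a change in study treatment/intervention regardless of grade". Protocol 6.2.6 sends the reader to 7.2 for AE collection requirements.

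Other sections are broader. Protocol 6.2.11 asks for AE information to be keyed within 72 hours of the site learning of the event, with no grade limit. Protocol 2.5 says participants will be monitored "with surveillance for and reporting of all AEs". Protocol 7.1 has all AEs reviewed weekly to decide which are treatment-related.

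On the analysis side, the secondary safety objective in Protocol 10.3 is "To compare the incidence of grade 2 or higher AEs and drug-related AEs between treatment arms", and the two endpoints are listed separately. SAP 2.2.2 repeats them as "Incidence of Grade 2 or higher AEs and drug-related AEs". Protocol 10.7.3.2 adds that "Occurrence of Grade 2 or higher AEs and drug related AEs will be evaluated using the same approach as outlined for the primary safety analysis". SAP 8.2 plans an "Overall Summary of TEAEs (Any TEAE, TEAE Related to study drug, Grade 2 or higher TEAE, Grade 3 or higher TEAE", with further rows, then tables of related TEAEs and of TEAEs by maximum severity on a scale that begins at mild. SAP 2.3 and SAP 11 make the safety presentation descriptive.

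**The concern.** An endpoint can be no more complete than the rule that collects it. A site that follows 7.2 to the letter may leave out a Grade 1 AE that did not change treatment, even if the investigator judges it related to study drug. That event belongs in the drug-related AE endpoint and in three kinds of SAP table. A site that works from 6.2.11 would enter it.

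In a descriptive safety analysis the incidence estimates are the whole result. If mild events are entered at some sites and not at others, the any-TEAE, mild and related rates would partly reflect recording practice. They would also compare poorly with Phase 1, where AEs were mostly mild. Protocol 3 and 10.9 say that emerging safety data help to choose doses for later parts, so the completeness of low-grade tolerability data has some practical weight.

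**Working it through.** **Step 1. Does 7.2 set a threshold, or only a deadline?**

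| Protocol section | Which AEs | Grade limit |
|---|---|---|
| 7.2 | Grade 2 or higher, or treatment changed; eCRF within 72 hours | Yes, except for treatment-changing AEs |
| 6.2.6 | Refers to 7.2 for AE collection | As 7.2 |
| 6.2.11 | AE information keyed within 72 hours | None |
| 2.5 | Reporting of all AEs | None |
| 7.1 | Weekly review of all AEs for relatedness | None |

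If 7.2 were only a deadline, its grade criterion would do no work, because 6.2.11 already sets the same 72 hours for AEs of any grade. The heading of 7.2 and the cross-reference in 6.2.6 also favour the threshold reading. But 7.2 nowhere says that Grade 1 AEs are not to be collected. The sections conflict, and a site could reasonably follow either.

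**Step 2. Which outputs depend on the answer?**

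- Covered by 7.2 on either reading: Grade 3 or higher AEs, related Grade 3 or higher AEs, AEs leading to discontinuation of treatment, and the Grade 2 or higher endpoint.
- Not fully covered under the threshold reading: drug-related AEs, any TEAE, related TEAEs by SOC and PT, and the mild category of the maximum-severity table.

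**Step 3. How large is the gap likely to be?** The only data in the documents are the Phase 1 results in Protocol 2.6. Assume mild = Grade 1 and moderate = Grade 2.

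First reproduce the printed percentages, using group sizes that add to the stated totals.

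- Single dose, 64 participants. Only 48 active and 16 placebo fits: any AE 17/48 = 35.4% and 7/16 = 43.8%; headache 6/48 = 12.5% and 3/16 = 18.8%.
- Multiple dose, 56 participants. A 42:14 split fits: any AE 18/42 = 42.9% and 7/14 = 50.0%; diarrhea 3/42 = 1/14 = 7.1%. Splits of 28:28 (12/28 and 14/28) and 14:42 (6/14 and 21/42) fit equally well. The 42:14 split is assumed because it matches the 3:1 ratio of the single-dose part.
- Food effect: 3 participants with an AE, all mild.

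Then count active participants with an AE, and those with an event that meets a 7.2 criterion.

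- With any AE: 17 + 18 + 3 = 38.
- Meeting 7.2: one with a moderate headache (single dose, 400 mg), one with moderate AEs in the 200 mg BID group (taken to be on active drug), and one with a mild rash that stopped dosing (800 mg, multiple dose). Total 3.
- Not required by 7.2: (38 − 3)/38 = 35/38 = 92%.
- With a 28:28 split: 17 + 12 + 3 = 32, and 29/32 = 91%.
- With a 14:42 split: 17 + 6 + 3 = 26, and 23/26 = 88%.

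**Step 4. The same count for drug-related AEs.** Protocol 2.6 describes one AE as related, the rash. It led to discontinuation, so the second 7.2 criterion captures it: 0 of 1 missed. No Phase 1 rate of related AEs is given, so the undercount of the drug-related endpoint cannot be calculated.

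**The case against.** The strongest reply is that 7.2 is a minimum and the protocol asks for more elsewhere. Protocol 6.2.11 asks for AEs to be keyed without regard to grade and says that study endpoints go on the eCRF, and drug-related AEs are a listed endpoint. The schedule of events has AEs at every visit. Protocol 7.3.4 calls for any worsened pre-existing condition to be recorded, and 7.3.1 puts clinically significant laboratory abnormalities on the AE page. This stands: one cannot say that nothing in the protocol asks for Grade 1 recording, or that such events would be missing. What remains is that the section named as the collection rule requires less than the endpoint needs.

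A second reply is that little depends on it. The primary safety endpoints and the Grade 2 or higher endpoint are fully covered, and the SAP, which supersedes the protocol's statistical section, tests no safety hypothesis. Diary symptom scores, including headache and diarrhea, and treatment-emergent laboratory grades are summarized separately from AE entries. The same rule also applies to every blinded arm. This stands too, and it limits the importance of the point. It does not make an any-TEAE or mild rate complete, and the diary and laboratory summaries carry no judgement of relatedness to study drug.

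A third reply is that the Phase 1 share describes AEs of any attribution in healthy volunteers and may not carry over to symptomatic patients. That is correct, and the figure is used only as a guide to scale.

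**Conclusion.** The collection rule in Protocol 7.2 does not support the drug-related AE endpoint or the SAP tables of any, related and mild TEAEs, and it conflicts with Protocol 2.5, 6.2.11 and 7.1. These descriptive incidences may be undercounted, by an amount that may differ with the section a site follows. Whether sites do differ cannot be known from the documents. About 9 in 10 active Phase 1 participants with an AE (35/38 = 92%; 88% to 91% under the other splits) had only events that 7.2 does not require. This rests on mild = Grade 1, moderate = Grade 2, and the participant with moderate AEs at 200 mg BID having received active drug.

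Three stronger readings are tempting and not supported. A reader might infer that most drug-related events of the kind seen in Phase 1 would be lost; the one related event described would be captured, and no related rate is given. A reader might infer that a dose trend in mild AEs is likely and would be hidden; Protocol 2.6 reports no trend with dose, and AEs were more frequent on placebo. A reader might infer that a formal between-arm comparison is compromised; SAP 2.3 and 11 leave none for safety.

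**What to change.** Reconcile Protocol 7.2 with 2.5, 6.2.11 and 7.1, and state plainly whether Grade 1 AEs are recorded. The smallest sufficient change for the endpoint is a third criterion in 7.2: all AEs assessed as related to study drug, whatever their grade. The any-TEAE and mild-severity tables then need one of two things: recording of all grades, with the 72-hour limit kept for the 7.2 categories if wished, or a table label that states the collection threshold.

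If data have already been collected under 7.2, label the drug-related endpoint and the TEAE tables in the SAP as covering Grade 2 or higher or treatment-changing AEs, and do not report any-TEAE or mild rates as complete.

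The cost of changing collection is slightly more eCRF entry, since the schedule of events already has AEs at every visit. Relabelling costs only SAP wording, but the stated endpoint becomes narrower.
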